**Post Treatment Period**

Activity	PT Week 4	PT Week 12	PT Week 24 or PT D/C a
Vital Signs and Weight	X	X	X
Hematology/Chemistry/Urinalysis/Coagulation Panel	X		X b
Pregnancy Test (urine) c	X (u)		X (u) b
Concomitant Medication Assessment d	X	X	X
PRO Instruments e		X	X
Adverse Event Assessment f,g	X	X	X
HCV RNA Sample	X	X	X
HIV-1 RNA h,i	X	X	X
HCV Resistance Sample	X	X	X
Flow Cytometry Sample h	X	X	X
Archive Plasma Sample	X	X	X

PT = Post Treatment

- a. Subjects who prematurely discontinue from the Post-Treatment Period should return to the site to complete the PT Discontinuation Visit procedures.
- b. Hematology/Chemistry/Urinalysis/Coagulation Panel and Pregnancy Test are not required at PT Week 24, but only at PT D/C if subject discontinued prior to PT Week 4.
- c. Urine Pregnancy testing is not required in the PT Period for women that are not of childbearing potential.
- d. Only medications taken for SAEs and treatment of HCV and HIV will be collected after 30 days post-dosing.
- e. PROs should be administered before any study procedures. PROs at PT WK 12 and PT WK 24 only required for subjects randomized to Arm A.
- f. All AEs (whether solicited or spontaneously reported by the subject) will be collected until 30 days post dosing.
- g. After 30 days following completion of study treatment, and throughout the Post-Treatment Period, all spontaneously reported SAEs will be collected (nonserious AEs will not be collected) (Section 6.1.4).
- h. HCV/HIV co-infected subjects only.

- i. For HCV/HIV co-infected subjects on stable ART: As detailed in Section 5.4.1.2, a repeat HIV-1 RNA blood draw to confirm a HIV-a RNA result of  $\geq 200$  copies/mL can be done as an unscheduled visit, but must be performed at least 2 weeks apart from the prior HIV-1 RNA result. At the time the repeat plasma HIV-1 RNA is drawn, a sample should be obtained for HIV-1 resistance testing. If the confirmatory HIV-1 RNA lab draw falls on the date of a scheduled study visit, only a single HIV-1 RNA and HIV-1 resistance blood draw is needed at the visit.

Note: Day 1 of the Post-Treatment Period will be defined as the day after the last dose of study drug.

## Appendix D. List of AIDS-Associated Opportunistic Infections

Collection of data regarding known AIDS-associated opportunistic infections is covered in Section 6.1.8.

- Aspergillosis
- Bartonellosis
- Candidiasis (\*Bronchi; \*Esophagus; \*Lungs; Oropharyngeal [Thrush]; \*Trachea; Vulvovaginal [Persistent, Frequent, or Poorly Responsive to Therapy])
- \*Coccidioidomycosis
- \*Cryptococcosis
- \*Cryptosporidiosis
- Cytomegalovirus (\*Retinitis; \*Cytomegalovirus Disease [other than liver, spleen or nodes])
- Enteric infections, Recurrent (Bacterial)
- Herpes Simplex Virus (\*Bronchitis; \*Esophagitis; \*Pneumonitis; \*Chronic Ulcer(s) [> 1 month in duration])
- \*Histoplasmosis
- Human Herpesvirus-8 Disease (Kaposi Sarcoma, Primary Effusion Lymphoma, Multicentric Castleman's Disease)
- Human Papilloma Virus Infections
- \*Isosporiasis (Cystoisosporiasis)
- Microsporidiosis
- \*Mycobacterium avium – Complex Disease (Disseminated)
- \*Mycobacterium tuberculosis – Infection and Disease
- \*Pneumonia
- \*Pneumonia, recurrent bacterial (and/or other respiratory infections including sinusitis, bronchitis, otitis)
- \*Progressive multifocal leukoencephalopathy (JC Virus Infection)
- Syphilis

- \*Toxoplasma Gondii Encephalitis
- Varicella Zoster Virus Diseases

\* AIDS-defining event as described by CDC Surveillance Case Definition of 1993.

[figure not shown]

3.0 Introduction

This statistical analysis plan (SAP) describes the statistical analyses to be completed by the AbbVie Statistics and Statistical Programming Departments for Study M15-592. Study M15-592 evaluates the efficacy, safety, and pharmacokinetics of ABT-493/ABT-530 in non-cirrhotic, chronic hepatitis C virus (HCV) genotype (GT) 1 to GT6-infected Asian adult subjects with or without human immunodeficiency virus (HIV) co-infection who are HCV treatment-naïve or treatment-experienced with interferon (IFN) (alpha, beta or pegylated-IFN [pegIFN]) with or without ribavirin (RBV) OR sofosbuvir (SOF) with RBV with or without IFN.

This SAP provides details to further elaborate statistical methods as outlined in Clinical Study Protocol M15-592 incorporating Administrative Change No. 1 dated 02 October 2017 and describes analysis conventions to guide the statistical programming. Analyses will be performed using SAS[®] Version 9.3 (SAS Institute, Inc., Cary, NC) or later under the UNIX operating system.

This SAP does not include the analysis plan for the pharmacokinetic data.

4.0 Study Objectives, Design and Procedures

4.1 Objectives

The primary objectives of this study are to compare, among the combined group of GT1 to GT6-infected subjects, among the GT1-infected subjects, and among the GT2-infected subjects, the percentage of subjects achieving SVR₁₂, (HCV RNA < lower limit of quantification [LLOQ] 12 weeks after the last actual dose of study drug) to a historical SVR₁₂ rate and to assess the safety following 8 or 16 weeks of treatment with the ABT-493/ABT-530 combination regimen in treatment-naïve and treatment-experienced non-cirrhotic adults with chronic HCV GT1 to GT6 infection with or without HIV co-infection.

The secondary objectives are to assess:

- The percentage of subjects with on-treatment HCV virologic failure;
- The percentage of subjects with post treatment relapse of HCV infection;
- The percentage of HCV/HIV co-infected subjects achieving SVR₁₂.

[figure not shown]
An additional objective is to assess the pharmacokinetics of ABT-493 and ABT-530 in Asian HCV-infected adults.

4.2 Design Diagram

This is a Phase 3, randomized, double-blind, placebo-controlled multicenter study to evaluate the efficacy and safety of ABT-493/ABT-530 in non-cirrhotic chronic HCV GT1 to GT6-infected Asian adult subjects with or without HIV co-infection who are HCV treatment-naïve or treatment-experienced with IFN (alpha, beta or pegIFN) with or without RBV OR sofosbuvir with RBV with or without IFN. This study consists of a Double-Blind (DB) Treatment Period, an Open-Label (OL) Treatment Period, and a Post-Treatment (PT) Period. The study schematic is presented in [Figure 1](#).

The study is designed to enroll approximately 504 subjects to meet scientific and regulatory objectives without enrolling an undue number of subjects in alignment with scientific and ethical considerations. A minimum of 150 GT1-infected subjects, a minimum of 150 GT2-infected subjects and approximately 60 GT3, 4, 5 or 6-infected subjects from China will be enrolled into this study. Approximately 105 GT1-infected subjects and approximately 39 GT2-infected subjects will also be enrolled into this study from the regional Asian countries of South Korea and Singapore. Of the approximately 504 subjects, a maximum of 50 HCV/HIV co-infected subjects will be enrolled.

Figure 1. Study Schematic

Chronic HCV GT1 – 6 infected adults without underlying cirrhosis will be enrolled into one of two treatment arms:

Arm A: ABT-493/ABT-530 300 mg/120 mg QD for 8 or 16 weeks

Arm B: Matching Placebo for 8 or 16 weeks followed by open-label ABT-493/ABT-530 300 mg/120 mg QD for 8 or 16 weeks

All subjects in this study are to be non-cirrhotic. Treatment experienced GT3-infected subjects will receive 16 weeks of treatment in the DB and/or OL Treatment Period; all other subjects will receive 8 weeks of treatment in the DB and/or OL Treatment Period.

In China, subjects will be randomized to receive active treatment (Arm A) or placebo (Arm B) in a 2:1 ratio for each of the GT1 and GT2-infected groups and the combined GT3 to GT6 infected group. In each regional Asian country, each of the GT1 and GT2 infected groups will be randomized in a 2:1 ratio.

Subjects who are randomized to Arm B will receive open-label ABT-493/ABT-530 300 mg/120 mg QD for 8 or 16 weeks following the DB Treatment Period.

Randomization of subjects will be stratified by geographic region (China, Singapore and South Korea), genotype (GT1, GT2, combined GT3 – 6), and HCV/HIV co-infection status (yes, no).

4.3 Sample Size

It is planned to enroll a total of approximately 504 subjects. In China, approximately 150 GT1-infected subjects will be randomized to receive active treatment (Arm A) or placebo (Arm B) in a 2:1 ratio; approximately 150 GT2-infected subjects will be randomized in a 2:1 ratio; and approximately 60 GT3, 4, 5, or 6-infected subjects will be randomized in a 2:1 ratio. Across Singapore and South Korea, approximately 105 GT1-infected subjects and approximately 39 GT2-infected subjects will be randomized to Arm A and Arm B; randomization will occur within each regional country in a 2:1 ratio. A maximum of 50 of the 504 subjects will have HCV/HIV co-infection across all countries. The expected approximate number of subjects by subpopulation is presented in [Table 1](#).

For the first primary endpoint, with a sample size of 336 GT1 – 6-infected subjects in the active treatment arm (Arm A) and assuming that 97% of these subjects will achieve SVR₁₂, this study has greater than 95% power to show non-inferiority to a historical control regimen, using a threshold of 90%, based on a 1-sample test for superiority using EAST 6.3. The threshold of 90% was based on a historical SVR₁₂ rate of 96% and a 6% non-inferiority margin (see Section 4.3.1). To establish efficacy, the lower bound of a 2-sided 95% confidence interval (CI) for the SVR₁₂ rate must be greater than 90% (based on a normal approximation of a single binomial proportion CI). No adjustment for dropouts is applicable because subjects who do not have data at PT Week 12 (after imputing) are counted as failures for SVR₁₂.

For the second primary endpoint, with a sample size of 170 GT1-infected subjects in the active treatment arm (Arm A) and assuming that 97% of these subjects will achieve SVR₁₂, this study has 90% power to show non-inferiority to a historical control regimen, using a threshold of 91%, based on a 1-sample test for superiority using EAST 6.3. The

threshold of 91% was based on a historical SVR₁₂ rate of 97% and a 6% non-inferiority margin (see Section 4.3.1). To establish efficacy, the lower bound of a 2-sided 95% CI for the SVR₁₂ rate must be greater than 91% (based on a normal approximation of a single binomial proportion CI). No adjustment for dropouts is applicable because subjects who do not have data at PT Week 12 (after imputing) are counted as failures for SVR₁₂.

For the third primary endpoint, with a sample size of 126 GT2-infected subjects in the active treatment arm (Arm A) and assuming that 96% of these subjects will achieve SVR₁₂, this study has greater than 80% power to show non-inferiority to a historical control regimen, using a threshold of 89%, based on a 1-sample test for superiority using EAST 6.3. The threshold of 89% was based on a historical SVR₁₂ rate of 95% and a 6% non-inferiority margin (see Section 4.3.1). To establish efficacy, the lower bound of a 2-sided 95% CI for the SVR₁₂ rate must be greater than 89% (based on a normal approximation of a single binomial proportion CI). No adjustment for dropouts is applicable because subjects who do not have data at PT Week 12 (after imputing) are counted as failures for SVR₁₂.

Table 1. Summary of Approximate Subject Numbers Expected by Subpopulation

Sub-Population	DB Active	DB Placebo	Total
GT1	170	85	255
China	100	50	150
HCV/HIV Co-infected	10	5	15
Not HCV/HIV Co-infected	90	45	135
Asian Regional Countries	70	35	105
HCV/HIV Co-infected	6	3	9
Not HCV/HIV Co-infected	64	32	96
GT2	126	63	189
China	100	50	150
HCV/HIV Co-infected	10	5	15
Not HCV/HIV Co-infected	90	45	135
Asian Regional Countries	26	13	39
HCV/HIV Co-infected	2	1	3
Not HCV/HIV Co-infected	24	12	36
GT3 – 6	40	20	60
China	40	20	60
HCV/HIV Co-infected	4	2	6
Not HCV/HIV Co-infected	36	18	54
Total GT1 – 6	336	168	504
China	240	120	360
HCV/HIV Co-infected	24	12	36
Not HCV/HIV Co-infected	216	108	324
Asian Regional Countries	96	48	144
HCV/HIV Co-infected	8	4	12
Not HCV/HIV Co-infected	88	44	132

4.3.1 Justification of Success Criteria for Primary Endpoints

For the first, second, and third primary endpoints, SVR₁₂ thresholds of 90%, 91%, and 89%, respectively were chosen to align with the historical control rates (and corresponding non-inferiority margins) used in the Global Phase 3 studies.

In the Global Phase 3 study of GT1-infected subjects without cirrhosis (Study M13-590), a historical control rate of 97% was used with a non-inferiority margin of 6%, resulting in a threshold of 91%. The historical control SVR₁₂ rate for non-cirrhotic subjects receiving ombitasvir/paritaprevir/ritonavir and dasabuvir (3-DAA) ± RBV in the 3-DAA Phase 3 trials among subjects dosed according to the United States Package Insert (USPI) and the Summary of Product Characteristics (SmPC) recommendations was 97% (870/894 patients),¹ with no difference between treatment-naïve and treatment-experienced subjects. Of note, the historical SVR₁₂ rate of 97% for the 3-DAA ± RBV regimen is identical to that of SOF/ledipasvir for 12 weeks in GT1-infected non-cirrhotic subjects (ION-1, ION-2, and ION-3).²

In the Global Phase 3 study of GT2-infected subjects without cirrhosis (Study M15-464), a historical control rate of 95% was used with a non-inferiority margin of 6%, resulting in a threshold of 89%. This historical control rate was based on the regimen of SOF + RBV for 12 weeks of treatment (Table 2).

Table 2. Historical Data for SOF + RBV for 12 Weeks, GT2-Infected Non-Cirrhotic Patients

Study	SVR ₁₂ n/N (%)
FISSION	59/61 (97%)
POSITRON	85/92 (92%)
FUSION	26/29 (90%)
VALENCE	59/63 (95%)
GS-US-334-011812 ³	132/136 (97%)
Total	361/381 (95%)

GT = genotype; RBV = ribavirin; SOF = sofosbuvir; SVR₁₂ = sustained virologic response 12 weeks postdosing
Note: SVR₁₂ rates from Sovaldi[®] (sofosbuvir) Tablets United States Package Insert.⁴

The Global Phase 3 study of GT3-infected subjects without cirrhosis (Study M13-594) was a randomized, active-controlled study, with the active control of SOF + daclatasvir (DCV) for 12 weeks. The assumption of an SVR₁₂ rate of 98% for the active control arm was based on the ALLY-3 study.⁵ Among non-cirrhotic subjects in the ALLY-3 trial, 98% of treatment-naïve subjects and 92% of treatment-experienced subjects achieved SVR₁₂ after 12 weeks of SOF + DCV treatment. Only treatment-naïve subjects were enrolled in Study M13-594. A 6% non-inferiority margin was used in Study M13-594.

The Global study of non-cirrhotic subjects which includes GT6 as well as GT4 and GT5 patients (Study M13-583) was an open-label single-arm study. The analysis of the primary endpoint (SVR₁₂) was descriptive only.

The historical SVR₁₂ rate for the first primary endpoint of the current study was calculated as a weighted average of the historical rates from the Global Phase 3 studies using the expected percentage of subjects for each GT, as indicated in [Table 3](#). The expected SVR₁₂ rate for the first primary endpoint was calculated similarly, using the expected rates for the test regimens in the Global Phase 3 studies. To align with the non-inferiority margin used in the Global studies, a non-inferiority margin of 6% was chosen for this study. Therefore, the percentage of subjects with SVR₁₂ will be non-inferior to the historical SVR₁₂ rate of 96% if the lower confidence bound of the 2-sided 95% CI for the percentage is > 90%.

The historical and expected SVR₁₂ rates for the second primary endpoint of the current study align with those from the Global Phase 3 Study M13-590. To align with the non-inferiority margin used in the Global studies, a non-inferiority margin of 6% was chosen for this study. Therefore, the percentage of subjects with SVR₁₂ will be non-inferior to the historical SVR₁₂ rate of 97% if the lower confidence bound of the 2 sided 95% CI for the percentage is > 91%.

The historical and expected SVR₁₂ rates for the third primary endpoint of the current study align with those from the Global Phase 3 Study M15-464. To align with the non-inferiority margin used in the Global studies, a non-inferiority margin of 6% was

chosen for this study. Therefore, the percentage of subjects with SVR₁₂ will be non-inferior to the historical SVR₁₂ rate of 95% if the lower confidence bound of the 2-sided 95% CI for the percentage is > 89%.

Table 3. SVR₁₂ Rates for Calculation of Historical and Expected SVR₁₂ Rates

	GT1	GT2	GT3	GT4 – 6	Overall
Historical SVR ₁₂	97%	95%	98%	95% ^a	96%
Expected ABT-493/ABT-530 SVR ₁₂	97%	96%	97%	95% ^a	97%
Weight	51%	37%	7%	5%	--

GT = genotype; SVR₁₂ = sustained virologic response 12 weeks postdosing

a. Global Study M13-583 did not provide estimates of these rates; 95% was chosen as a conservative estimate.

4.4 Planned Analyses

The primary analysis will occur after all subjects in Arm A have completed the PT Week 12 Visit or prematurely discontinued the study. The primary analysis will summarize data through PT Week 12 for Arm A subjects and data through the DB Treatment Period for Arm B subjects. The data for the primary analysis will be locked after data cleaning, and data collected after this lock will be added to a new version of the database. Results from the primary analysis will be described in the primary clinical study report (CSR) and submitted to regulatory agencies as part of an NDA submission.

An interim analysis will occur after all Arm A subjects have completed the PT Week 24 Visit or prematurely discontinued the study and all Arm B subjects have completed the PT Week 12 Visit or prematurely discontinued the study. The data for the interim analysis will be locked after data cleaning, and data collected after this lock will be added to a new version of the database.

The final analysis will be conducted after all subjects enrolled in the study have completed the PT Week 24 Visit or prematurely discontinued the study. The data for the final analysis will be cleaned and locked at the end of the study and included in the final CSR.

All analyses will be conducted by statisticians and programmers at AbbVie (or their designees) according to the methodologies specified in this SAP. There is no intention of shortening the follow-up time of subjects based on efficacy findings from the primary or interim analyses. All subjects who receive active study drug will be followed for 24 weeks following treatment. Therefore, no statistical adjustment will be employed due to the primary or interim analysis.

5.0 Analysis Populations

5.1 Definitions of Analysis Populations

Within each of the populations defined below, subjects who are GT1-infected and GT2-infected will be categorized as such. The categorization of these 2 groups will be based on the latest determination of genotype from the baseline sample (by the central laboratory or by phylogenetic analysis, with preference given to the phylogenetic analysis results) at the time of the primary SVR₁₂ analysis.

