5.1.2 Modified Intention-to-Treat (mITT) Populations

Sensitivity analyses of SVR₁₂ as described in Section 10.5, when applicable, will be performed on the ITT population modified to exclude subjects who have multiple GTs according to the central laboratory or phylogenetic analyses of the baseline sample or subjects who received an incorrect duration of treatment due to incorrect classification of

GT or treatment experience at randomization (mITT-GT), and on the mITT-GT population modified to exclude subjects who did not achieve SVR₁₂ for reasons other than virologic failure (i.e., subjects with reasons other than on-treatment HCV virologic failure and relapse) (mITT-GT-VF).

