5.2 Variables Used for Stratification of Randomization

Randomization of subjects will be stratified by geographic region (China, Singapore and South Korea), genotype (GT1, GT2, combined GT3 – 6), and HCV/HIV co-infection status (yes, no).

If a subject was randomized based on incorrect stratification information, the correct stratification information (if known at the time of the primary SVR₁₂ analysis) will be used to define subpopulations for analyses.

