10.8 HCV and HIV Resistance Analyses

For subjects who enroll in South Korea or Singapore, full length NS3/4A and NS5A from baseline samples will be sequenced by next generation sequencing (NGS). For subjects who enroll in South Korea or Singapore who experience HCV virologic failure (on-treatment HCV virologic failure or post-treatment relapse as defined in Section 10.1), full length NS3/4A and NS5A genes from the first sample after virologic failure with HCV RNA \geq 1000 IU/mL will be sequenced by NGS. For resistance analysis only, the last

sample collected before OL Day 1 will be considered the baseline sample for Arm B subjects. For genotype 1-infected subjects experiencing virologic failure who enroll in China, amino acids 1 – 181 in NS3 and 1 – 215 in NS5A from the baseline sample and the first sample after virologic failure with HCV RNA ≥ 1000 IU/mL will be sequenced by population sequencing. An appropriate subtype-specific prototypic reference sequence will be used for comparison with sequences from samples. Subjects who experience HCV virologic failure will be referred to as subjects in the primary virologic failure (PVF) population, and a listing by subject that includes HCV subtype, IL28B genotype, reason for SVR₁₂ non-response, time point(s) sequenced as closest to time of HCV virologic failure, and HCV RNA value at the HCV virologic failure time point(s) will be produced for these subjects. In addition, all listings described below will display HCV subtype, and reason for SVR₁₂ non-response in the subject identifier for each subject. A separate listing will delineate all subjects in the PVF population for whom no sequencing was performed (e.g., lost to follow-up while HCV RNA ≤ 1000 IU/mL).

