Analysis 3: In subjects who enroll in South Korea or Singapore, the SVR₁₂ rate will be calculated and compared using Fisher's exact test between subjects with or without polymorphisms at 15% detection threshold in NS3 only, in NS5A only, any in NS3, any in NS5A, any in NS3 or NS5A, any in NS3 and NS5A at the *key subset of amino acid positions*. Analysis will be performed by HCV genotype, subtype, and overall on the mITT-GT-VF population.

Analysis 4: The following analyses will be performed for subjects who enroll in South Korea or Singapore who do not achieve SVR₁₂ (with separate summaries for subjects in PVF and non-PVF populations) and have post-baseline resistance data available:

- Listings by subject of all *treatment-emergent substitutions* relative to the baseline amino acid sequences will be provided for each DAA target (NS3 and NS5A).
- Listings by subject of all *substitutions at signature amino acid positions* in a post-baseline time point for each DAA target (NS3 and NS5A).

Analysis 5: For subjects who enroll in China who experience virologic failure and have sequence data available, the following analyses will be conducted:

- A listing of all baseline polymorphisms at signature amino acid positions for each DAA target (NS3 and NS5A).
- Listings by subject of all post-baseline substitutions relative to the baseline amino acid sequence will be provided for each DAA target (NS3 and NS5A).
- Listings by subject of all emerged substitutions, by amino acid position and substitution within a DAA target in a post-baseline sample relative to the baseline amino acid sequence will be provided for each DAA target (NS3 and NS5A).
- Listings by subject of all post-baseline substitutions at signature amino acid positions relative to the appropriate prototypic reference amino acid sequence will be provided for each DAA target (NS3 and NS5A).

If resistance-associated substitutions are not detected in a given target for a subject at the time of failure/discontinuation, then that target may not be sequenced in subsequent samples from that subject.

HCV Genotype/Subtype

Phylogenetic analysis will be conducted on HCV sequence from all available baseline samples from subjects who enroll in South Korea or Singapore and genotype 1-infected

subjects experiencing virologic failure who enroll in China in order to accurately determine subtype.

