Subjects' HCV genotype and subtype may be assessed based on the Inno-LiPA 2.0 Assay used by the Central lab (Covance), the HCV genotype determination by Sanger sequencing a region of NS5B by the Central lab (Covance) and/or from phylogenetic analysis of the full length NS3/4A, and/or NS5A sequences performed by AbbVie. If the phylogenetic analysis is available, then it will be used to determine the subject's HCV genotype and subtype. If it is not available, then the Sanger sequencing assay result will be used to determine the subject's HCV genotype and subtype, if available. Finally, if neither the phylogenetic analysis result nor the Sanger sequencing assay results is available, then the Inno-LiPA assay results will be used to categorize the subject. This subtype information will be presented in summaries of efficacy subgroup analyses. The baseline characteristic summary will use the results from the central laboratory (Sanger sequencing or Inno-LiPA 2.0 Assay [if Sanger sequencing not available]).

A summary of HCV genotype subtype as provided by the central laboratory (Sanger sequencing or Inno-LiPA 2.0 Assay [if Sanger sequencing not available]) versus phylogenetic analysis also will be provided.

HIV Drug-Resistance Analyses

If any subject on stable HIV-1 ART develops a confirmed, quantifiable plasma HIV-1 RNA level (HIV-1 RNA \geq 200 copies/mL at one assessment and \geq 500 copies/mL on repeat testing) after starting the study, the HIV-1 protease, reverse transcriptase and/or integrase sequences, as applicable, will be analyzed by Monogram Biosciences using the GenoSure[®] Prime drug resistance assays for subjects from South Korea and Singapore. The number of subjects who demonstrate HIV genotypic resistance and the genotypic resistant mutations detected in the samples obtained from these subjects will be tabulated and summarized in the final CSR, as applicable. Resistance will be defined as described by the IAS-USA Panel.⁹

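### Genotype for the GT1 and GT2 primary groups prefers phylogeny, which in China is planned only for GT1 virologic failures, so for Chinese GT1 subjects group membership partly depends on outcome

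*SAP*

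**What the plan says.** SAP section 5.1 applies one classification rule inside every analysis population, including the ITT population used for the primary endpoints. A subject is GT1 or GT2 according to the latest genotype of the baseline sample at the time of the primary SVR12 analysis, "by the central laboratory or by phylogenetic analysis, with preference given to the phylogenetic analysis results". Section 10.8 gives the same hierarchy: "If the phylogenetic analysis is available, then it will be used to determine the subject's HCV genotype and subtype". Sanger sequencing comes next and the Inno-LiPA assay last.

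Section 10.8 also says whose samples are analysed:

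- **South Korea and Singapore:** "Phylogenetic analysis will be conducted on HCV sequence from all available baseline samples from subjects who enroll in South Korea or Singapore".
- **China:** only genotype 1-infected "subjects experiencing virologic failure who enroll in China in order to accurately determine subtype". The sequencing plan matches: partial NS3 and NS5A regions are sequenced "For genotype 1-infected subjects experiencing virologic failure who enroll in China". Baseline sequencing is added for Chinese GT1 subjects lost to follow-up before 6 weeks while not suppressed, who are also non-responders.

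Two further rules use the same information. The mITT-GT population (section 5.1.2) is formed to "exclude subjects who have multiple GTs according to the central laboratory or phylogenetic analyses of the baseline sample", among other exclusions. Section 5.2 replaces wrong stratification data with "the correct stratification information (if known at the time of the primary" SVR12 analysis.

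Section 10.3 tests the GT1 and GT2 groups as the second and third ranked primary endpoints. Success requires a lower 95% bound above 91% and 89% respectively, using the normal approximation unless the observed rate is 100%.

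**The concern.** The analysis set for a confirmatory test should not depend on the outcome being tested. For Chinese GT1 subjects it does, in part. Virologic failure triggers the phylogenetic analysis, and its result can override the genotype on which the subject was enrolled.

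A Chinese GT1 failure found to be another genotype leaves the GT1 denominator. If re-typed as GT2, it is added to GT2 as a failure. If found to carry several genotypes, it is dropped from mITT-GT. A Chinese GT1 responder with the same typing error stays where it was, because nobody looks. Within China this route can raise the GT1 rate and lower the GT2 rate, but not the reverse.

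Two primary endpoints are at stake, and because testing is in fixed sequence the GT1 result also decides whether GT2 is tested at all. SAP section 10.5 contains no analysis of the GT1 or GT2 endpoints by central-laboratory genotype that would show whether the conclusion depends on this rule.

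**Working it through.** **Inputs.** Arm A GT1 n = 170, of whom 100 are from China; Arm A GT2 n = 126 (SAP Table 1). Assumed GT1 SVR12 97%, threshold 91%, stated power 90% (SAP section 4.3). Decision rule: lower bound = p − 1.96·√(p(1−p)/n) (SAP section 10.3). Earlier 8-week GT1 non-cirrhotic data: 383/387 responders, 1/387 on-treatment failures, 0/384 relapses (Protocol Table 5).

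**1. The plan's own figure.** A one-sample normal test with null variance at one-sided 0.025 gives

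Φ{[(0.97 − 0.91) − 1.96·√(0.91·0.09/170)] / √(0.97·0.03/170)} = Φ{(0.06 − 1.96·0.02195)/0.01308} = Φ(1.298) = 90.3%.

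This reproduces the stated 90%. The sample size is not in dispute.

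**2. How many failures GT1 can absorb, and what one reassignment does.**

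| Responders/n | Rate | Lower bound | Against 91% |
|---|---|---|---|
| 161/170 | 94.71% | 91.34% | passes |
| 160/170 | 94.12% | 90.58% | fails |
| 160/169 | 94.67% | 91.29% | passes |
| 159/170 | 93.53% | 89.83% | fails |
| 159/169 | 94.08% | 90.53% | fails |
| 159/168 | 94.64% | 91.24% | passes |

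Up to 9 failures of 170 are allowed. With 10, removing one failure reverses the decision; with 11, removing two does.

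**3. The GT2 side (threshold 89%).** 118/126 gives 89.39% and passes. Adding one Chinese GT1 failure re-typed as GT2 gives 118/127, lower bound 88.45%, which fails. The same rule can therefore count against the drug on the third endpoint.

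**4. How many subjects are exposed.** At 97% SVR12, China contributes 100 × 0.03 = 3 Arm A GT1 non-responders. That is a ceiling, because only virologic failures go to phylogeny, while dropouts and missing data also count as SVR12 failures. In Protocol Table 5, 387 − 383 = 4 subjects did not respond, and 1 of those was a virologic failure. Applying that share gives 3 × 1/4 = 0.75 subjects; applying the virologic failure rate directly gives 100 × 1/387 = 0.26. Both rest on very few events.

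**5. Effect on the chance of GT1 success.** The discordance rate is not in the documents, so a range is assumed. Let each of 170 subjects fail independently, with a share 100/170 of failures in China. Let a proportion v of those be virologic, and a proportion m of the virologic ones be reassigned out of GT1. Exact binomial calculation under the planned rule gives:

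| True SVR12 | v | m = 0 | 1% | 2% | 5% | 10% |
|---|---|---|---|---|---|---|
| 91% | 1 (upper bound) | 5.25% | 5.50% | 5.76% | 6.60% | 8.23% |
| 91% | 1/4 | 5.25% | 5.31% | 5.38% | 5.57% | 5.89% |
| 97% | 1 (upper bound) | 96.67% | 96.78% | 96.89% | 97.20% | 97.67% |
| 97% | 1/4 | 96.67% | 96.70% | 96.73% | 96.81% | 96.94% |

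The 5.25% at m = 0 comes from the normal-approximation interval itself, not from this concern. The chance of exactly 10 failures, where one reassignment matters, is 1.9% at a true 97% and 4.1% at a true 91%.

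**The case against.** **Size.** The strongest objection is that the effect is very small. It needs a virologic failure in China, a discordance at genotype rather than subtype level, and a result at the margin. The calculations support this: with one quarter of failures virologic and up to 5% reassigned, the chance of success moves by 0.32 points at a true 91% and 0.14 points at a true 97%. That stands, and it is why the point is not graded higher.

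**Whether the override applies in China.** Section 10.8 gives the purpose of the phylogeny as determining subtype, and its hierarchy speaks of full-length sequences, while the Chinese sequences are partial. The authors may not have meant a Chinese result to change genotype. But section 5.1 makes no exception, and section 10.8 applies the hierarchy to genotype as well as subtype. The doubt is itself a reason to settle the wording.

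**Existing safeguards.** The first-ranked GT1-6 endpoint does not depend on genotype assignment. The SAP also tabulates central-laboratory against phylogenetic genotype, so a discordance would be visible. Neither shows what the GT1 or GT2 decision would be under an outcome-independent genotype.

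**Stronger readings.** A reader might infer that the GT1 rate can only rise and the GT2 rate can only fall. That holds only for the Chinese route. About 70 GT1 and 26 GT2 Arm A subjects come from South Korea and Singapore, where responders and failures can both move. A reader might also infer that Chinese GT2 failures can never be re-typed. The documents do not settle this: SAP section 10.1 uses phylogenetic comparison with baseline to separate relapse from reinfection in any subject, and Protocol section 8.1.4 plans baseline sequencing for all virologic failures. Finally, a Wilson bound should not be used to show fragility: Wilson decides the primary test only at 100%, and under the planned rule 162/170 passes with a lower bound of 92.11%.

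**Conclusion.** The concern holds in a limited form. As written, the SAP lets the outcome decide which Chinese GT1 subjects (about 100 of 170 in Arm A) can be reclassified, and therefore who is counted in the GT1 and, through transfers, GT2 primary groups and in mITT-GT.

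The expected distortion is small: at most about 3 exposed Chinese Arm A GT1 subjects at 97% SVR12, and probably fewer than 1 if the earlier 8-week data are a guide. These figures assume that China enrols as planned and that its subjects fail at the same rate as the rest. The discordance rate is an assumption throughout. The documents do not support reading this as a material bias in the expected result.

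What makes it worth correcting is that one reassigned failure can reverse a confirmatory decision (160/170 against 160/169), that the trigger is the endpoint itself, and that no planned analysis would resolve the question. It should be fixed, but is not a defect that undermines the trial.

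**What to change.** Define the GT1 and GT2 groups for the primary endpoints, and the multiple-genotype exclusions of mITT-GT, from the central-laboratory genotype: Sanger where available, otherwise Inno-LiPA. This is obtained at Screening whatever the outcome, and section 10.8 already uses it for the baseline summary. Use phylogenetic genotype in a sensitivity analysis of the GT1 and GT2 endpoints, limited to countries where all available baseline samples are sequenced. Align sections 5.1, 5.1.2, 5.2, 10.6 and 10.8, and state in 10.8 whether a Chinese phylogenetic result can change genotype or only subtype.

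The cost is wording; no new samples or data are needed. The downside is that a few subjects known to be mis-typed stay in their screened genotype group in the primary analysis, and that the regional phylogenetic results, which do not depend on outcome, inform only the sensitivity analysis.
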